Study Title: Smoking Treatment and Exercise Program for Underserved Populations (STEP UP)

Clinical Trials Identifier: NCT02873754

Protocol and Statistical Analysis Plan, 4/3/2017

Title: Mobile Health Intervention to Help Low-Income Smokers Quit Smoking and Increase Physical Activity

Principal Investigator: [name].

Background

Cigarette smoking and physical inactivity are the two greatest behavioral health risks leading to chronic disease and premature death in the U.S. (Department of Health and Human Services, 2004). Smoking alone accounts for 1 in 5 deaths, and physical inactivity, coupled with poor diet, accounts for 1 in 6 (Mokdad, Marks, Stroup, & Gerberding, 2004). Both smoking and physical inactivity are more prevalent in low-income populations (Hiscock, Bauld, Amos, Fidler, & Munato, 2012; Powell, Slater, Chaloupka, & Harper, 2006). Moreover, both frequently co-occur (Kaczynski, Manske, Mannel, & Grewal, 2008), thereby compounding their deleterious effects (Strine, Balluz, & Ford, 2007; Ferrucci et al., 1999). In light of this co-occurrence, a number of researchers have tested combined smoking and exercise interventions and found that they convey better outcomes than stand-alone smoking-cessation efforts (Weinstock, Barry, & Petry, 2008; Ussher, Taylor, West, & McEwen, 2000).

Contingency management (CM) is an intensive behavioral therapy that provides positive reinforcers (e.g., vouchers, money) to individuals contingent upon utilization of an intervention or demonstration of an outcome, often abstinence in the case of substance users. CM is a particularly powerful tool for generating behavioral change in low-income populations due to the greater inherent value of monetary incentives (Lynagh, Sanson-Fisher, & Bonevski, 2013). CM has demonstrated strong short-term efficacy in the treatment of substance use, with effect sizes eclipsing those of other behavioral treatments (Dutra et al., 2008). Incentive-based exercise interventions may be similarly effective for increasing exercise, with one study (Kurti & Dallery, 2013) demonstrating that rewarding participants with as little as \$1.00 a day for meeting daily step goals increased the odds of meeting exercise objectives by a factor of 6.42.

Unfortunately, traditional applications of CM for smoking and other substance misuse have been hampered by the need for clinic-based verification of abstinence, which represents a major barrier to treatment for low-income populations (Gornick et al., 1996). As a result, these approaches have largely been relegated to inpatient and day-treatment programs. Our laboratory, however, has developed a smartphone application (app) which allows participants to video themselves multiple times daily while using a small carbon monoxide (CO) monitor and to transmit the data to a secure server. This innovation has made the use of CM for outpatient smoking cessation portable and feasible as well as highly efficacious in treating smoking in vulnerable populations (Hertzberg et al., 2013; Carpenter et al., 2015).

Financial incentives have similarly been applied to exercise interventions with positive short-term effects. The majority of such trials have tested the effect of directly incentivizing weight loss via varying combinations of diet and exercise (Volpp et al., 2008; Abrahms & Allen, 1974; Harris & Bruner, 1971; Jeffery et al., 1993; Jeffery et al., 1984). According to a recent meta-analysis of financial-incentive trials (Mantzari et al., 2015), the mean 6-month odds ratio (OR) for diet/exercise interventions was 1.66 (95% CI=1.28-2.15). Incentives to participate in physical activity have also been applied with slightly smaller effects (Charness & Gneezy, 2009; Jeffery, Wing, Thorson, & Burton, 1998; Pope & Harvey-Berino, 2013). However, a major drawback of these interventions is that they require extensive face-to-face contact between participants and

study personnel. Furthermore, despite immediate short-term gains, significant long-term effects on weight loss or engagement in physical activity were observed in none of these studies (Mantzari, 2015). Still, incentives may be particularly effective at promoting short-term increases in physical activity, which are expected to be beneficial during a smoking quit attempt. Note that the purpose of the physical-activity target in this project is to enhance smoking-cessation outcomes (and other secondary outcomes such as increased steps and improved mood) rather than weight control expressly.

In light of recent advances in the development of mobile interventions for exercise (Fanning, Mullen, & McAuley, 2012) and evidence that treating physical inactivity concurrently with smoking may increase short-term abstinence above and beyond typical smoking interventions (Spring et al., 2009), we have designed a Smoking Treatment and Exercise Program for Underserved Populations (STEP UP) that uses mobile CM (mCM) to simultaneously promote smoking cessation and physical activity.

The purpose of this pilot project is to evaluate the feasibility, acceptability, and efficacy of STEP UP. Given the heightened prevalence of smoking and physical inactivity among low-income populations, in addition to structural barriers to treatment, we propose to target low-income smokers with this intervention.

Methods

Participants

Participants will be adult men and women who smoke cigarettes. We plan to enroll 15 participants in order to reach a goal of 10 study completers.

Participants will be eligible for inclusion in the study if they meet the following criteria:

- current household income less than twice the federal poverty guidelines (Finer & Henshaw, 2006; for instance, someone from a family of 4 must have a household income less than \$48,500 to be eligible)
- currently smoke >10 cigarettes a day
- smoking for at least the past year
- can speak and write fluent conversational English
- are 18-70 years of age
- are willing to make an attempt to quit smoking and increase physical activity

Participants will be excluded from the study for the following:

- inability to walk
- expected to have unstable medication regimen during the study
- currently receiving non-study behavioral treatment for smoking
- myocardial infarction in the past 6 months
- contraindication to nicotine replacement therapy (NRT) or bupropion with no medical clearance
- exclusive use of other forms of nicotine such as cigars, pipes, e-cigarettes, or chewing tobacco
- current pregnancy

- current imprisonment or psychiatric hospitalization

Recruitment

Participants will be recruited from outpatient clinics at Duke University Medical Center (DUMC). Flyers and brochures will be placed in DUMC clinic areas, and may also be placed in community settings such as local restaurants and grocery stores. We will also advertise in local newspapers and online classified services such as www.craigslist.com. We will contact administrators and/or clinicians at local area community health centers, including Lincoln Community Health Center, to get permission to provide recruitment materials at those sites. Upon approval by the Durham Veterans Affairs (VA) Medical Center IRB, we will post flyers and brochures at that facility and its community-based outpatient clinics. Any flyer posted at the VA-owned facilities will include the following statement: "This is not VA research, will not be conducted by VA, has not been reviewed by VA's Institutional Review Board, and is not endorsed by VA. VA is not responsible for any costs incurred by a Veteran if the Veteran enters the study as a research subject. The announcement is being provided for information only."

Any participant who contacts by telephone the study coordinator or other study staff regarding the study will be provided more information, and will be interviewed using an IRB-approved telephone screening. We will retain the deidentified telephone screening information for all callers so that we can analyze data regarding telephone screen-outs in order to determine recruitment and inclusion/exclusion feasibility.

Study Procedures

Table 1 provides a summary of study procedures, including the timing and location of each session and payments associated with them.

Table 1. Study Procedures

Session #	Location of Visit	Procedures	Payment
1	Lab	Consent; questionnaires; urine drug screen and pregnancy test; carbon monoxide readings; equipment training; counseling session 1 of 5	\$100
1-3 weeks			
2	Phone	Brief phone check-in for participants using bupropion; begin bupropion if eligible	n/a
1 week			
3	Phone	Counseling session 2 of 5; begin practice mCM monitoring	n/a
1 week			
4	Phone	QUIT DATE; counseling session 3 of 5; begin 4 weeks active mCM monitoring; begin nicotine replacement therapy (NRT)	n/a

1 week			
5	Phone	Counseling session 4 of 5; continue active mCM monitoring	n/a
1 week			
6	Phone	Counseling session 5 of 5; continue active mCM monitoring	n/a
2 weeks			
7	Phone or Text Message	Begin 1 week mCM wash-out period	Up to \$798 mCM compensation
2 weeks post-mCM treatment follow-up			
8	Phone	Questionnaires; equipment return; treatment adherence measures	\$50 for equipment return
3 months after Session 1			
9	Phone/Lab	Questionnaires; return to lab and provide a saliva sample if abstinence reported	\$25 for assessment; \$50 for saliva sample
6 months after Session 1			
10	Phone/Lab	Questionnaires; return to lab and provide a saliva sample if abstinence reported	\$25 for assessment; \$50 for saliva sample
TOTAL COMPENSATION POSSIBLE			\$1098

Once a participant reports to the laboratory to begin the study, the study staff member obtaining consent will explain the study in detail, provide the participant with an IRB-approved written consent form explaining the procedures and risks, and answer any questions. The initial consent process and documentation takes place in a quiet, private office at DUMC (Hock Plaza space), and participants are given the chance to thoroughly read the consent prior to participation. Participants are given a copy of the signed informed consent form, and are given phone numbers to call if they have additional questions about the consent form or the research, if they have any problems during the study, or if they have questions about participating in research studies in general. No study procedures will begin until informed consent has been obtained.

After providing informed consent, potential participants will provide a breath sample to assess CO level, and will complete measures (see Measures section herein) regarding mood, exercise and smoking history, and sociodemographic data. Urine samples will also be used to screen for illicit drug use (to document use). Because the study drugs are each Category C drugs, urine pregnancy tests will also be completed for women of childbearing potential. We have developed a short interview for female participants; this interview will help us determine which female participants must have a urine pregnancy test, and when the test should be done. Female participants of childbearing potential who are not pregnant must agree to use appropriate

contraception during the course of the study, and to notify study staff if they become pregnant during the study.

All enrolled participants will receive a tele-health intervention that combines evidence-based telephone cognitive behavioral therapy (CBT) for smoking cessation, access to nicotine replacement therapy (NRT) and bupropion, and intensive CM therapy administered via a smart-phone based application (mCM). The treatment components are separately described below. After randomization, participants will be given study equipment, including a smartphone (with the condition-appropriate app already installed), CO monitor, Jawbone UP2 fitness tracker, and a high-accuracy digital bathroom scale. Participants will receive training in use of all equipment at the screening visit. Participants will also complete session 1 of the CBT in person in order to enhance therapeutic rapport-building.

Study Devices. Smart phones to be used in this study are the DROID MAXX 2. The phone has an octa-core 1.7 Ghz processor, 2 GB RAM, and 5.5" full HD display. The operating system (OS) being utilized for the smart phones is Android 5.1.1 Lollipop, see FIPS 140-2 certificate 1998. The STEP UP mobile phone app is an adaptation of smoking-cessation mCM mobile phone apps that have been used in several IRB-approved studies (PRO0031703, PRO0050835, PRO0048990, PRO0061683, PRO0062101) with expert input from [name]. [name] is a Professor in the Duke University Department of Medicine and the Associate Director of Research at the Durham VA Geriatric Research, Education, and Clinical Centers. [name] is an exercise physiologist and her specialization is in the design and execution of behavioral clinical trials of physical activity.

We have modified the app to include physical-activity monitoring components and feedback. Step-tracking will be implemented via a Fitbit Flex 2 fitness tracker. The Fitbit Flex 2 is a light-weight wristband capable of tracking physical activity, including steps. Data are transmitted from the Fitbit Flex 2 to the smart phone via Bluetooth technology and the Fitbit Flex 2 App. Our STEP UP mobile app will pull the data from Fitbit's servers and integrate the data with smoking cessation data so that participants and study staff can monitor progress towards step goals. Within the STEP UP app, progress toward daily step goals will be conveyed twice daily at semi-random intervals and will also be available on-demand. The mCM manual includes the participant instructions, payment schedules, and app screenshots.

The CO breath monitor to be loaned to participants is the Bedfont/coVita iCO™ Smokerlyzer®. The device is a battery operated instrument that measures CO in ppm (http://www.bedfont.com/shop/smokerlyzer/ico_smokerlyzer). The Bedfont/coVita iCO™ Smokerlyzer® plugs into a smart phone by means of the headphone jack, and communicates with the smart phone app developed by our team. Participants are able to see the CO reading within the app, and the app collects the CO data directly. Data are stored in the same manner as the videorecordings that participants upload (see below and in "Protection From Risks: Data Security" herein).

With regards to FDA device issues, Bedfont/coVita will not be seeking 510k Clearance on the iCO™ Smokerlyzer® because it does not meet the standard/criteria of a medical device. Device manufacturers are required to follow FDA guidance to inform them of when a device necessitates 510k application. Per [name] at Bedfont/coVita, their regulatory team has determined that this is not necessary primarily because they do not make a medical claim about

the device, as it is not designed to diagnose a disease or illness. Simply measuring CO is not diagnosing a disease or illness and Bedfont/coVita makes no medical claim that the iCO™ Smokerlyer® can be used to screen for CO poisoning.

Text Messaging Within the App. Our group has developed a text-messaging support library for smoking cessation in collaboration with the Department of Veterans Affairs (VA) Public Health Group and NCI (US Department of Veterans Affairs & National Cancer Institute, 2013). This library is in use by the VA and was launched nationwide May 2013. As of June 1, 2015, 2,867 smokers had enrolled in the SmokeFreeVET smoking-cessation program that utilizes this support library. We will also use a physical-activity text-message library developed by Drs. [name] and [name] that is currently being used by the GetFitVET program, an 8-week exercise intervention for veterans. Pilot data was collected from 10 lower-income individuals ranging from 23 to 65 years old who were interviewed regarding the content and wording of the individual messages and keywords in the library. All reported using a cell phone, with the majority using text-message communication daily. Qualitative data from these participants were used to modify the messages and keyword categories (e.g., framing messages from a positive stance, shorten messages). We recently completed a second pilot study with 15 participants, 5 earning under \$30,000 annually. According to this study, messages providing encouragement were endorsed over those detailing the benefits of exercise and those pertaining to goal-setting.

Mobile CM Procedures. Participants will use the smart phone app, CO monitor, and Fitbit Flex 2 wristband step-tracker to participate in the contingency management portion of the study. The STEP UP intervention includes (1) a 1-week training period in which participants are compensated simply for uploading videos and wearing the wristband step-tracker, (2) a 4-week period of active mCM in which they are compensated based on their own CO readings and physical-activity levels (i.e., meeting step goals), and (3) a 1-week fading period in which participants are compensated for uploading videos, regardless of their CO readings, and for wearing the wristband step-tracker, regardless of steps taken. Reinforcement amounts are detailed in the mCM manual provided to participants. Participants will be eligible to earn up to \$798 across the 6-week intervention and monitoring period.

After the one-week training period, participants will be compensated for CO readings suggesting abstinence and wearing the step-tracker, and will be rewarded a bonus for abstinent CO readings + reaching step goals established by the counselor. Because reinforcers are most effective when delivered immediately after the target behavior is performed (Lattal, 2010), the phone app is designed to allow therapists to provide quick feedback on abstinence status, financial amount earned, and how the amount was calculated.

In order to verify smoking abstinence, participants will use the smart phone app to provide video recordings of him/herself taking CO readings. For each video recording, participants will be asked to 1) begin a recording using the smartphone device; 2) breathe in and hold his/her breath for the duration of the countdown shown on the screen; 3) when prompted, expel all air from lungs into the CO monitor while being video-recorded; 4) hit submit to upload the encrypted video recording using encrypted network connections to the secure server.

Through the smart-phone app, participants log-in to a secure website to upload their video recordings and see personalized information regarding their reinforcement information. Study coordinators can monitor validity and compliance on a daily basis and offer feedback to ongoing

participants regarding compensation so they are well-practiced at the procedures by the time contingent reinforcement is initiated. During the practice week, participants will be compensated \$1 (twice per day) for a valid smoking reading. After the practice week, monetary reinforcement becomes contingent on abstinence, operationally defined as CO readings that are < 6 ppm (after the first week). In the first week of abstinence, smoking cessation compensation will be based not on CO < 6ppm, but on a proportion of participant's baseline CO as defined by Lamb (Lamb, Morral, Kirby, Iguchi, & Galicka, 2004). Because an escalating, versus a fixed reinforcement schedule has produced higher abstinence rates (Heil et al., 2008; Stoops et al., 2009), an escalating schedule will be used in this protocol.

With regards to reinforcement for physical activity, participants are reinforced \$1 each day he/she wears the step-tracker. In addition, participants will be assigned daily step goals derived based on baseline practice-week activity level. Participants recording under 5,000 steps per day at baseline will be given an initial goal of increasing their daily steps by 500 steps during the first week (Tudor-Locke & Bassett, 2004; Tudor-Locke, Craig, Thyfault, & Spence, 2013). Participants recording 5,000 steps or more per day will be given an initial goal of increasing their daily steps by 1,000 steps. Daily step goals will increase accordingly each week (i.e., by 500 steps per day if under 5,000 or by 1,000 steps per day if 5,000 or over; Tudor-Locke & Bassett, 2004; Tudor-Locke, Craig, Thyfault, & Spence, 2013). If participants fail to reach daily step goals 4 of 7 days of a given week, their daily step goals will not be increased the following week. Participants who meet their step goal on a given day will receive a bonus if they have also remained abstinent from smoking. Failure to meet the daily step goal will result in the normal abstinence-contingent payment without the bonus. No reward will be provided for participants who meet their daily step goal but fail to demonstrate abstinence, as the primary goal of the intervention is to increase exercise in the service of promoting smoking cessation.

Participants will be asked to return the smart phone and fitness tracker at the end of the treatment period. Participants will be allowed to keep the CO monitor since it has a limited number of uses. To ensure that participants return the phone and fitness tracker, we are providing postage paid return mailers and adding a \$50 incentive for equipment return.

Cognitive Behavioral Therapy for Smoking Cessation. Both the STEP UP and comparison condition will receive a participant manual and 5 sessions of cognitive-behavioral telephone counseling focused on smoking-cessation and increasing physical activity. The smoking-cessation content is consistent with the Public Health Service Clinical Practice Guide, and is the same used in our published pilot studies and currently funded mCM trials (R01CA037220; 1I01HX001109; 1I01RX001301). The physical-activity portion of the manual and participant workbook are based on telephone-counseling content used in clinical trials exercise interventions run by [name] at Duke University Medical Center and the Durham VA Medical Center.

Pharmacotherapy for Smoking Cessation. Treatment will include standard pharmacotherapy for smoking cessation. This consists of bupropion, nicotine patch, and an 8-week course of ≤ 2 rescue methods (i.e., nicotine gum or lozenge) in participants who are medically eligible to take them. Participants will begin bupropion use two weeks prior to the scheduled quit date, and will be asked to continue using the medication until the 6-month follow-up. Participants will be screened for suitability for NRT and bupropion. If any participant reports a contraindication to NRT or bupropion and reports having a primary care physician, the study coordinator and/or study physician, [name], PhD, will attempt to contact the physician for medical

clearance. If no contact from the primary healthcare physician can be made, the participants' health information will be evaluated by the study physician, [name]., Ph.D., who will provide medical clearance (or not) to participate in the trial and to use smoking-cessation pharmacotherapy. Study medications will be provided via mail.

Text-Messaging Support. Text-messaging support has been shown to provide a small effect on decreasing smoking and increasing physical activity. Both arms will receive text messages *via* the app (i.e., not *via* a SMS paid plan). Specifically, participants will receive one smoking-cessation and one physical-activity message (randomly selected from a general library that includes 178 messages) per day during the intervention period. Text messages will be delivered as part of the smart phone app. Participants will also receive content-specific messages upon entering key phrases (i.e., "no time", "bad weather", "pain", "cravings", "smoked", "stress") associated with 83 additional messages.

Post-Treatment Session and 3-Month and 6-Month Follow-Up. To eliminate the burden of travelling to study appointments for assessments, telephone surveys will be conducted at the end of the mCM/mobile assessment phase. At that phone visit, participants will complete measures (read aloud by study coordinator) about treatment acceptability, smoking, medication adherence, self-efficacy to quit/remain quit, and physical activity.

Participants will be contacted by phone at 3- and 6-months post-screening visit. During the phone visit, participants will complete measures (read aloud by study coordinator) about smoking, medication adherence, self-efficacy to quit/remain quit, and physical activity. If participants report smoking abstinence at the 3 and 6-month follow-ups, they will be asked to come to the laboratory to provide a saliva sample and CO reading to bioverify smoking abstinence. If any participant is unable to come to the laboratory, he/she will be asked to provide a saliva sample by mail. When saliva is collected by mail, participants are sent instructions, saliva vials, a brief tobacco use assessment (that includes use of nicotine replacement therapies in the prior week), and a postage-paid padded envelope for returning the sample to the study coordinator. At each time point, any participant who provides a saliva sample will be paid \$50. All sample identification will be with an assigned study number rather than patient identifiers. Saliva samples will be mailed to Salimetrics, LLC for cotinine assay (see "Smoking-Cessation Outcome Measures and Biochemical Verification" herein).

Participant Reimbursement. Participants who drop out will receive partial reimbursement for the time and effort they devote to the study. Because monetary reinforcement is an essential part of the intervention we are studying, participants will receive payments as reinforcers during treatment in addition to payments they receive to compensate for their time and effort on the study. Participants are paid: 1) \$100 for completion of the screening visit and mCM training; 2) up to \$798 for mCM; 3) \$50 for equipment return at the end of treatment; 4) \$25 each for the assessments at 3- and 6-month follow-up; and 5) \$50 (each) for provision of saliva samples at 3- and 6-month follow-up. Participants could be paid up to \$1098 for their complete participation.

Study Measures

Table 2 outlines measures to be given at each time point in the study.

Table 2. Study Measures and Schedule of Administration

	Baseline	Weekly	PT*	3 Months	6 Months
Background Variables					
Demographics	X				
Fagerström Test of Nicotine Dependence	X		X	X	X
Minnesota Nicotine Withdrawal Scale			X	X	X
General Smoking History Questionnaire	X				
NRT & Bupropion Contraindications	X				
Stanford 7-Day Physical Activity Recall	X		X	X	X
Intrapersonal Variable					
Short Form 36 Health Survey	X		X	X	X
Global Self-Efficacy for Quitting Smoking	X		X	X	X
Readiness-to-Change Questionnaire	X		X	X	X
NRT & Bupropion Self-Efficacy	X		X	X	X
Physical Activity Self-Efficacy	X		X	X	X
Social Support	X		X	X	X
Positive and Negative Affect	X	X	X		
Physical Vigor	X	X	X		
Process Measures					
Treatment-Acceptability Survey			X		
Use of Smoking-Cessation Aids		X	X	X	X
Morisky Adherence Questionnaire		X	X	X	X
Outcome Measures					
Prolonged Abstinence: 7-day		X	X	X	X
Prolonged Abstinence: 30-day				X	X
Quit Attempts			X	X	X
Timeline Follow-Back-Quit Attempts			X	X	X
Steps (Assessed by Step-Tracker)	X	X	X		

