Self-reported and bioverified prolonged abstinence from smoking at the 3 and 6-month follow-up will be the primary end-point. Prolonged abstinence will exclude tobacco use in the first two weeks following the quit date to give participants time to achieve initial abstinence (Hughes et al., 2003). Self-reported prolonged abstinence will be verified by cotinine assay, a metabolite of nicotine in the saliva. Saliva samples will be collected from participants who report prolonged abstinence at each follow-up. They will be mailed to Salimetrics LLC for saliva cotinine assays. Saliva samples will be analyzed for the presence of cotinine using a standard cut point of 10 ng/ml to determine abstinence. A blind sample of 5% will be run again to assure test accuracy of saliva samples. Secondary smoking outcomes will include 7- and 30-day point prevalence abstinence at each assessment, where abstinence is defined as no tobacco use in the prior 7 or 30 days, respectively.

Data Analyses

Descriptive statistics will be used to summarize all study variables, including smoking history and current use, nicotine-dependence level, self-efficacy, readiness to change, and social support. For continuous variables, means, standard deviations, ranges, and histograms will be generated. For categorical variables, frequencies and proportions will be generated. Individual and mean trajectory plots of the longitudinal outcome variables will be constructed to understand their general trends over time (i.e., post-treatment, 3- and 6-month follow-ups). We will examine all variables to determine if parametric distributional assumptions (e.g., normality for the continuous variables) are valid. Variables not meeting distributional assumptions will either be transformed or modeled using non-parametric or semi-parametric methods (e.g., quasi-likelihood methods; McCullagh & Nelder, 1989). In order to describe the compliance/completion of the sample in terms of smoking-cessation aids and intervention completion, these variables will be summarized. In terms of descriptors for outcome measures, we will record number of quit attempts, quality of life, and number of weekly steps, and utilize time-line follow-back data to identify when participants may have lapsed. Potential covariates (e.g., age, gender, minority status) will be evaluated for inclusion in models. If any of these variables have a significant bivariate effect on treatment outcomes, they will be entered first in statistical models.

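### No written eligibility or analysis rule uses the pre-quit CO readings to confirm smoking, so a near non-smoker who overstates smoking could be counted as a verified quitter

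*Combined protocol and SAP*

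**What the plan says.** **Entry.** Under Methods, Participants, the two criteria on smoking history are "currently smoke >10 cigarettes a day" and "smoking for at least the past year". Neither carries a biochemical threshold, and no exclusion criterion mentions CO or cotinine. Under Recruitment, people who call about the study "will be interviewed using an IRB-approved telephone screening".

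**Session 1.** Under Study Procedures, after consent, "potential participants will provide a breath sample to assess CO level". Table 1 lists for this visit "urine drug screen and pregnancy test; carbon monoxide readings; equipment training; counseling session 1 of 5", along with consent and questionnaires. No minimum CO is given, nothing follows from a low value, and no baseline saliva or cotinine is listed.

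**Payment.** Under Mobile CM Procedures, abstinence for payment is "operationally defined as CO readings that are < 6 ppm" once the first active week is over. In that first week payment depends on a proportion of the participant's baseline CO.

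**Endpoint.** Both sections on biochemical verification make prolonged abstinence at 3 and 6 months the primary endpoint. It is self-reported and then verified by saliva cotinine at a "standard cut point of 10 ng/ml to determine abstinence".

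**The concern.** The plan verifies abstinence biochemically but has no written rule for verifying smoking. The payment limit from active week 2 and the cotinine cut point are fixed values, and neither requires a fall from the participant's own starting level. Someone who hardly smokes can be below both before treatment begins and still be below both at follow-up.

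There is a reason to overstate smoking. A participant can receive up to $1,098, and the Background argues that incentives work well in low-income populations "due to the greater inherent value of monetary incentives". At stake is the meaning of the abstinence rate. With 15 people planned, one person who had nothing to quit moves it visibly, and this pilot is meant to evaluate efficacy and to inform a larger trial.

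**Working it through.** **Stated figures.** Payments (Participant Reimbursement; Table 1): 100 + 798 + 50 + 2 × 25 + 2 × 50 = $1,098, as stated. Of this, 1,098 − 798 = $300 lies outside mCM. Planned size (Participants): 15 enrolled to reach 10 completers. No expected quit rate is given.

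**Tracing one entrant.** Take a near non-smoker who reports more than 10 cigarettes a day and reads 4 ppm at Session 1 (an illustrative value).

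1. Eligibility: no written CO criterion is failed.
2. Practice week: readings are taken, but no entry or analysis rule refers to them.
3. Active week 1: payment is relative to baseline CO, so it is not automatic.
4. Active week 2 onward: 4 < 6, so the CO condition is met with no change in behaviour.
5. Follow-up: to count as a verified quitter, the person must also report prolonged abstinence, give saliva and pass the cotinine cut point. No baseline cotinine exists for comparison.

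**Effect on a single-group rate.** Let n be the number analysed, p the true quit rate among genuine smokers (assumed) and k the number of such entrants, each taken as certain to be counted abstinent.

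Expected rate = [k + (n − k)p]/n

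Bias = k(1 − p)/n, so each entrant adds (1 − p)/n.

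| Assumed p | n = 15, k = 1 | n = 10, k = 1 |
|---|---|---|
| 10% | 0.9/15 = 6.0 points | 0.9/10 = 9.0 points |
| 20% | 0.8/15 = 5.3 points | 0.8/10 = 8.0 points |
| 50% | 0.5/15 = 3.3 points | 0.5/10 = 5.0 points |

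At p = 20% and n = 15, the expected rate goes from 20% to 25.3% with one such entrant and to 30.7% with two. The n = 10 column takes the entrant to be among the completers.

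**How likely is one?** The documents give no frequency. If a proportion q of enrollees were of this kind, the chance of at least one among 15 is 1 − (1 − q)^15: 14% at q = 1%, 26% at 2%, 54% at 5% and 79% at 10%. All four values of q are assumptions.

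**Effect of excluding them.** With n = 15, k = 1 and p = 20%, removing the entrant from numerator and denominator gives an expected (14 × 0.20)/14 = 20%, which is p again.

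**The case against.** The case against is substantial, and much of it limits the point.

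- **Self-report.** A reader might infer that entry demonstrably rests on self-report alone. The documents do not show that. CO is taken while people are still potential participants, the reimbursement section calls this the screening visit, and careful screening against the criteria is promised. The telephone script and the mCM manual are not in the documents. What can be said is that no threshold is written in the eligibility list.
- **Practice week.** Payment there is for a valid reading of smoking, which could be taken as a check. It is a payment condition that applies after enrolment, and elsewhere Mobile CM Procedures describes that week as paid just for uploads and tracker wear.
- **Low CO and cotinine.** It is tempting to treat a low CO as leading straight to verified abstinence. Nothing in the documents says that a CO below 6 ppm implies cotinine below 10 ng/ml. A light smoker who carries on smoking would have to misreport abstinence and pass a separate assay. The endpoint route realistically concerns non-smokers and near non-smokers.
- **Money.** A reader might suppose that such a person collects most of the $798. No share can be computed: the amounts are in the mCM manual, the schedule escalates, the bonus also needs step goals, and first-week payment depends on baseline CO.
- **Pilot status.** The study is small, its analysis is largely descriptive and no efficacy threshold is set. This bears on how much weight the point deserves, but does not remove the gap.

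**Conclusion.** The point holds as a cheap improvement. The written plan collects pre-quit CO, uses it only to set first-week payment, and then judges payment from week 2 and the primary endpoint against absolute limits. A near non-smoker could therefore enrol and be counted as a verified quitter.

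Per entrant, the upward bias is 6.0 to 3.3 percentage points at n = 15 and 9.0 to 5.0 points at n = 10. This assumes true quit rates of 10% to 50% and an entrant who completes every verification step. The simple shares 1/15 = 6.7% and 1/10 = 10% might be read as the bias. They are only its ceiling, reached if no genuine smoker quits, because the entrant takes a place that a genuine smoker could have filled.

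A reader might also infer that the bias always favours the intervention. That is so for a single-group abstinence rate. Study Procedures says that all enrolled participants receive mCM, but other sections refer to randomization and a comparison condition without giving arm sizes. If arms were compared, such entrants in both arms would raise both rates and could dilute the difference.

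How often this would happen is unknown.

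**What to change.** **Preferred.** Add one eligibility line: a Session 1 CO at or above the trial's own abstinence limit (6 ppm) before equipment is issued, with one repeat reading allowed.

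**Minimum.** Keep entry as written and pre-specify that abstinence is reported twice: for all enrolled, and excluding from numerator and denominator anyone with no reading of 6 ppm or more at Session 1 or in the practice week. Both sets of readings precede the quit date in Table 1, so the exclusion does not depend on outcome. State the number excluded.

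**Cost.** One line of text, using measurements already planned, plus an occasional repeat breath reading. Under the preferred option, an occasional true smoker with a low reading needs a repeat or is lost. Under the minimum option, such a person drops out of the second analysis only. Neither option closes the gap fully: a CO floor does not itself establish baseline cotinine or consumption above 10 cigarettes a day.
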